Patients who are identified as eligible will be screened using a survey if they are interested in participating. First, they will be asked if they sometimes drink alcoholic beverages. If yes, they will be asked how many times in the past month they have had 5 or more drinks in a day (for men) or 4 or more drinks in a day (for women). They will also be asked if, on any week in the past month, they have had more than 14 drinks (for men) or more than 7 drinks (for women). If they answer yes to either of those questions, they are considered to be an at-risk drinker and will qualify for the study. This screening may also be conducted over the phone if the participant indicates interest in the study but is unable to complete the screening procedure while visiting the clinic. If the screening procedure indicates that the participant is eligible, they may begin the study within 30 days time.

Subject Exclusion Criteria: Individuals who are HIV-negative, less than 18 years of age, who are not identified as an at-risk drinker through the alcohol screener, or who are not currently prescribed HIV medication will not be eligible to participate. For the randomized controlled trial, participants who have not had their viral load tested within the 3 months prior to beginning the intervention (3 months before baseline for the Intervention group, 3 months before the 8-week time point for the Waitlist-Control group) will not be eligible to begin the study until they have had bloodwork completed. Additionally, participants will take the AUDIT questionnaire as part of the study screener. If they score a 20 or higher, indicating alcohol dependence, they will not be eligible for study participation.

Study Recruitment

After screening, patients who are deemed eligible for the study may be recruited in the following ways:

- An IRB approved letter mailed to the patient and then after two weeks the patient may be contacted over the phone or in person at a clinic visit about the study unless they decline
- Through an approved study flyer or direct patient initiated contact to the study coordinator
- A clinic provider refers patient to study or gives patient study flyer at clinic visit

- Direct patient contact in the clinic at clinic visit
- Outreach to a patient who has previously signed an informed consent form for another research study which allowed for future contact

Study Intervention/Investigational Product

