7. The research coordinator will check to see if the following inclusion criteria are met:
 - a. HIV-positive
 - b. 18 years or older
 - c. An at-risk drinker as identified by the alcohol screener
 - d. Currently taking HIV medication
 - e. A score less than 20 on the AUDIT questionnaire
 - i. Score is displayed on the final page of the questionnaire. If above 20, see step 9 below for further direction.
8. If patients are eligible, the research coordinator will provide them with a TRAC flyer and consent form
 - a. If the patient wants to enroll in the study, the coordinator will proceed with enrollment (see next section)
 - b. If the patient does not want to enroll today, they can take the TRAC flyer and consent form with them. If they want to enroll at a later date, they can call the VA coordinator.
 - c. They are eligible to begin the study if they enroll within 30 days. If they would like to join the study after that date, they will need to be re-screened.
9. If patients are ineligible because of a score of 20 or higher on the AUDIT questionnaire, a note will be made in their chart and a referral made to their clinical team for follow-up regarding concerning levels of alcohol use.
10. Screening activities will not collect any data to be used in the study.

Step 2: Patient Enrollment

1. The coordinator will go through the consent form and HIPAA form with the participant, discussing:
 - a. The overall purpose of the study
 - b. The time commitment of the study
 - c. Their expectations as a participant
 - d. The incentives they will receive
 - e. Any questions the participant has
2. Once the participant has demonstrated sufficient understanding of the consent and HIPAA forms, the research coordinator will obtain consent and a signature on the HIPAA form.
3. The research coordinator will assign the participant a numeric identifier and record it in the secure code key
 - a. The research coordinator will inform the participant that if they forget their study ID at any time, they can contact the researchers to learn what it is.
4. Only researchers will have access to this key, which will be kept in a password-protected file

5. The research coordinator will then check the randomization spreadsheet (pre-generated set of random numbers for each participant ID assigning them to the intervention or waitlist-control group)
 - a. If they are in the intervention group (Group 1):

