 - i. The research coordinator will check the participant's medical record to make sure they have had their viral load tested within the previous 3 months. If not, their entry in the study will be delayed until after they have obtained viral load testing.
 - ii. The research coordinator will inform the participant that they have been placed in the Intervention group.
 - iii. The coordinator will schedule the participant's first videoconferencing session (1 ½-2 hours) with the study interventionist using the shared calendar, where they will receive their smartphone (if needed) and breathalyzer
 - iv. The research coordinator will provide the participant with a copy of the Participant Manual, which includes instructions for downloading the breathalyzer app on to their own phone, if they choose to use it.
 - v. The coordinator will encourage the participant to try downloading the app, and tell them that the interventionist will be in touch soon and can help them to install the app if need be
 - b. If they are in the waitlist-control group (Group 2):
 - i. The research coordinator will check the participant's medical record to make sure they have had their viral load tested within the previous 1 month (within 3 months of the intervention starting), or has plans to get it tested within the following 2 months. If not, their entry in the study will be delayed until after they have obtained viral load testing.
 - ii. The research coordinator will inform the participant that they have been placed in the waitlist-control group
 - iii. The participant will be provided the chance to complete the baseline assessment at that time on a laptop computer. If they choose not to complete it, the interventionist will call them to provide introductions and give them the web address for completing the questionnaire. This web address will also be provided to the participant on a handout.
6. The research coordinator will ask the participant the following questions about their cell phone:
 - a. Do you prefer to use a study phone or your own phone? (Study Phone/Own Phone)
 - b. If they prefer to use their own phone:
 - i. Do you own a smartphone? (Y/N)
 1. If no, inform participant that they must use a study phone, which will be provided at their first appointment
 - ii. What type of phone is it? (Android/iPhone/Windows/Other)

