2. Upon arrival to the clinic for the first intervention session, the patients will be shown to a private room to begin their first videoconferencing session
3. The patient will be given a laptop to complete the initial assessment battery
4. If the participant is in need of a study phone, the VA coordinator will provide this phone, along with the breathalyzer, to the participant
5. Participants will begin the first intervention session, which will consist of the following content/tasks:
 - a. Introductions and orientation to the technology (smartphone and breathalyzer, stored at the clinic; tutorial handouts provided)
 - b. Review of self-monitoring procedures and setting of "do not disturb" hours
 - c. Review of breathing awareness exercise
 - d. Scheduling follow-up intervention sessions for weeks 2-8, conducted via mobile phone
 - e. A short post-session satisfaction survey, delivered via text message and completed immediately following the session.
6. The day after the first session, participants will begin self-monitoring their alcohol, medication use, and mental health
 - a. They will be texted at two random times each day using an automated software to complete a breathalyzer reading and finish a survey
 - b. If participants do not respond to the request within 30 minutes, a text reminder will be sent, followed by another an hour later.
 - i. If the participant is in a situation where they are unable to complete the breathalyzer test, they will be able to respond to the text message and request a follow-up reminder two hours later.
 - c. If participants wish to go to sleep for the night and have not yet received their evening reminder, they can elect to complete a breathalyzer reading and survey before going to bed.
 - d. Self-monitoring will continue through the end of week 8 (until they return to the VA to complete their post-test and return their equipment)
 - e. Participants will be instructed to call the interventionist if they have any technical difficulties throughout the course of the study
7. Sessions 2-8 of the intervention will be conducted via phone call, with patients instructed to find a private room at home from which to speak with their counselor.
 - a. After each session, the participant will complete a short post-session satisfaction survey, delivered via text message and completed immediately following the session

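### Allocation is opened before an arm-specific viral-load entry check and before the baseline battery, and the SAP defines no week-8 analysis set for delayed or never-started participants

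*Combined protocol and SAP*

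**What the plan says.** Step 1, item 7 of the protocol lists what is verified before enrolment: HIV status, age, at-risk drinking, current HIV medication and AUDIT score. Viral-load recency is not on that list.

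Step 2, item 5 follows consent and ID assignment: "The research coordinator will then check the randomization spreadsheet (pre-generated set of random numbers for each participant ID". The viral-load check sits beneath that look-up, in one version per arm. Item 5a(i) asks for a test within the previous 3 months in the intervention arm. Item 5b(i) asks on the waitlist for "viral load tested within the previous 1 month (within 3 months of the intervention starting), or has plans to get it tested", the planned test falling within the following 2 months. The consequence of failing is the same in both arms: "If not, their entry in the study will be delayed until after they have obtained viral load testing". No maximum delay is given; the 1-week limit under Study Schedule concerns study visits.

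Subject Exclusion Criteria explains why the arms differ. The window is "3 months before baseline for the Intervention group, 3 months before the 8-week time point for the Waitlist-Control group". The same paragraph bars a participant without such a test from beginning until the bloodwork is complete.

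Participants are told their group at items 5a(ii) and 5b(ii). The baseline battery comes afterwards. For the intervention arm it is at the first clinic session (Step 3a, item 3): "The patient will be given a laptop to complete the initial assessment battery". For the waitlist (Step 3b, item 1) it follows randomisation, at enrolment, at home, or at an appointment in the next 30 days.

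The Statistical Analysis Plan compares the two groups over the 8-week period by Kruskal-Wallis, ANOVA and Cohen's d. It names no analysis population, and its two missing-data scenarios are for daily survey responses.

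**The concern.** Week 8 is the only randomised comparison in this trial. After it the waitlist starts the intervention, and the SAP pools the arms. That comparison is protected when everything that decides who enters has been settled before the arm is known. Here one entry condition is applied after the look-up, and it depends on the arm. The same patient may therefore start at once in one arm and wait in the other. If some of those who wait never start, or are left out of the analysis, the arms compared at week 8 are no longer the arms that were randomised. The SAP does not say whether such participants count.

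Two related matters come from the same ordering. The baseline battery, which includes self-reported alcohol use, is answered by people who already know their group. And Subject Exclusion Criteria requires completed bloodwork before beginning, whereas Step 2, item 5b(i) admits a waitlist participant on a plan alone, so the two places disagree.

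The trial is a pilot that disclaims power, but its stated aim is effect sizes as preliminary evidence of efficacy. Recruitment and engagement are also feasibility objectives, so delays and non-starts by arm are results in their own right.

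**Working it through.** **There is no figure to reproduce.** The goal of 50 participants has no power, effect-size or SD calculation behind it.

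**Which patients are treated differently.** Cross time since last test with whether a test is planned in the next 2 months, and apply items 5a(i) and 5b(i):

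| Last test | Planned test | Intervention arm | Waitlist arm |
|---|---|---|---|
| within 1 month | yes | enters | enters |
| within 1 month | no | enters | enters |
| 1-3 months ago | yes | enters | enters |
| 1-3 months ago | no | enters | **delayed** |
| over 3 months ago | yes | **delayed** | enters |
| over 3 months ago | no | delayed | delayed |

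Two of the six types are discordant, in opposite directions.

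**Whether the arm difference is an accident.** It is not. With 1 month taken as 30 days, 30 + 56 = 86 days, inside 3 months (about 91 days). The waitlist's 1-month window therefore agrees with a 3-month window before its own intervention start.

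**Possible size at week 8.** The documents give no frequencies, loss rates or outcome differences, so everything below is assumed:
- 1:1 allocation with 25 per arm (the ratio is not stated)
- p, the share of patients of a discordant type: 0.10 to 0.30
- d, how far that type differs from all other patients in drinking: 0.3 to 0.5 SD
- r, the share of the delayed type that never starts and is dropped: 0.30 to 0.50 for the waitlist type (no test planned), 0.10 to 0.30 for the intervention type (test planned)

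After loss, the type's share in its arm falls from p to p(1 - r)/(1 - pr). The arm mean therefore shifts by d × [p - p(1 - r)/(1 - pr)].

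- Waitlist type, low: 0.3 × [0.10 - 0.07/0.97] = 0.3 × 0.0278 = 0.008 SD
- Waitlist type, high: 0.5 × [0.30 - 0.15/0.85] = 0.5 × 0.1235 = 0.062 SD
- Intervention type, low: 0.3 × [0.10 - 0.09/0.99] = 0.3 × 0.0091 = 0.003 SD
- Intervention type, high: 0.5 × [0.30 - 0.21/0.91] = 0.5 × 0.0692 = 0.035 SD

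Participants lost, p × r × 25: 0.75 to 3.75 on the waitlist and 0.25 to 2.25 in the intervention arm.

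The standard error of the difference is √(2/25) = 0.283 SD. The largest single-type shift is 0.0618/0.283 = 0.22 SE, and for the intervention type 0.0346/0.283 = 0.12 SE. The direction may be either way. If every delayed participant starts and is analysed, the shift is zero.

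**Baseline timing.** The SAP's week-8 comparison names no baseline term, so arm-aware baselines touch it only if it is baseline-adjusted. The later pooled models use change from baseline, but no size can be put on that from the documents.

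**The case against.** The strongest reply is that nothing in the protocol says anyone is lost: the check delays entry and does no more. The medication, drinking, age and AUDIT criteria, as well as consent, are all settled before the look-up. In each arm the check (item i) comes before the participant is told the group (item ii), so someone delayed need not yet know the arm. A waitlist participant also passes on a plan, so arranging a routine test may be enough, and 30-50% never starting may be too pessimistic. The trial is an unpowered pilot, and one SAP sentence would close most of the gap. All of this stands. It limits the size of the problem, but it does not supply the missing analysis set or make entry independent of arm.

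Three stronger readings are tempting and are not supported.

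- **Adding the two types together.** At the upper settings this gives 0.0618 + 0.0346 = 0.096 SD if the types differ from other patients in opposite directions. That supposes 60% of all patients are discordant, and the sum becomes 0.138 SD if the difference is measured against the concordant 40% instead. With the same direction the shifts partly cancel, to 0.027 SD. No combined figure should be relied on. Likewise, if 30% of one arm never entered and differed from entrants by 1 SD, the shift would be 0.30 SD, but the documents give no ground for such values.
- **Re-screening on drinking after allocation.** Subject Inclusion Criteria says of eligible patients that "they may begin the study within 30 days time", and Step 1, item 8c says "They are eligible to begin the study if they enroll within 30 days" and "If they would like to join the study after that date, they will need to be re-screened". A reader might infer that a randomised patient awaiting a test must be screened again. Allocation takes place inside the enrolment step, so such a patient has plausibly enrolled already, and item 8c does not obviously apply.
- **Compromised concealment.** Custody of the randomisation list is not described. That is a missing detail, and it does not show that allocation was foreseeable.

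**Conclusion.** The point holds as a cheap improvement. On the text, allocation precedes an entry check that differs by arm, two patient types are delayed in one arm only, both arms know their group before the baseline battery, and the SAP leaves the week-8 set undefined. Subject Exclusion Criteria and Step 2, item 5b(i) also need reconciling on whether a planned test is enough.

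The text does not show that the week-8 estimate will be biased. Bias requires that delayed participants be lost or dropped. Under the assumed ranges, with 25 per arm, a single type moves the effect size by at most about 0.06 SD (0.22 SE). That is small beside the sampling error of a trial this size. The case for acting is that the protection costs little and covers the only randomised contrast.

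**What to change.** 1. **Protocol, Step 2.** Complete the viral-load check, by one rule applied alike to everyone, and the baseline battery before the randomization spreadsheet is opened. Where the COVID-19 pathway applies, the battery can be done remotely, as that pathway already allows. Reconcile Subject Exclusion Criteria, Step 2 items 5a(i) and 5b(i), Step 3a item 13 and Step 3b item 16 with that check. The choice of window is the sponsor's.
2. **SAP.** Analyse all randomised participants as randomised at week 8, seek week-8 questionnaires from those who never start, and report delays and non-starts by arm.

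**Cost.** The changes are to wording and need no added staff. The enrolment visit lengthens by the 45-60 minute battery, and Session 1 shortens correspondingly for the intervention arm. That arm's $30 baseline payment moves from Session 1 to enrolment, with no change in total. Some randomisations will come later or be lost, which matters because recruitment is a feasibility objective.

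Each common window has a price. With 3 months, a waitlist viral load could be about 91 + 56 = 147 days old at intervention start. With 1 month it is at most about 30 + 56 = 86 days, but patients tested 1-3 months ago, who now pass in the intervention arm, would need a repeat test or a wait.

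If the sponsor prefers to keep the arm-specific windows, item 2 and moving the baseline battery ahead of the look-up still stand.
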